### **Investigator Training**

Prior to screening subjects for this study, the PI, sub-Investigators, study coordinators, and other designated staff (as applicable) will be provided information on study execution, data collection, and procedures specific to this clinical protocol.

### **Monitoring**

This study will be monitored by the Sponsor to ensure:

- The rights and well-being of the subjects are protected;
- Reported data is accurate, complete, and verifiable from source documents where utilized; and
- The conduct of the study is in compliance with the currently approved protocol/amendment(s), applicable GCPs, and with applicable local/regional regulatory requirements.

The extent and nature of monitoring will be predetermined and agreed to by the Sponsor and investigators. Monitors will comply with established written standard operating procedures as well as procedures (i.e., monitoring plan) specified by the Sponsor for monitoring this study as characterized in the monitoring plan.

#### **4.4 PROTOCOL DEVIATIONS**

A deviation (any activity conducted outside the parameters established by the protocol) can be identified from a number of sources. Potential sources for identification of deviations include but are not limited to: a member of the Investigator's staff, a Sponsor representative during monitoring visits, or a member of the data management or statistical groups when entering or analyzing data. Regardless of the source, it is crucial to document the deviation. The PI will report protocol deviations to the IRB as required by the IRB/EC procedures.

### **5.0 STATISTICAL METHODS PLANNED IN THE PROTOCOL AND DETERMINATION OF SAMPLE SIZE**

#### **5.1 STATISTICAL AND ANALYTICAL PLANS**

The Sponsor Data Management and Biostatistics groups will be responsible for the analysis of data from this protocol. A comprehensive and detailed Statistical Analysis Plan will be finalized prior to database lock to supplement the statistical design and analysis described in this section.

Categorical variables will be summarized descriptively by frequencies and associated percentages. Continuous variables will be summarized descriptively by number of subjects, mean, standard deviation, median, minimum, and maximum. Confidence intervals will also be provided for procedure-related variables.

#### **5.2 STUDY DESIGN**

This prospective open-label, multicenter, clinical study will evaluate the intra-operative performance of the powered circular stapler used in left colectomy procedures in a post-market setting.

#### **5.3 TREATMENT ASSIGNMENT**

Upon site initiation, subjects will have procedures completed using the powered stapler, as described in Section 3.9.

#### **5.4 INTERVAL WINDOWS**

No interval windows are specified for this study given the short-term nature of follow-up.

## **5.5 PRIMARY ENDPOINT AND ASSOCIATED HYPOTHESES**

The primary endpoint is the number of subjects in whom a stapler performance issue is observed, where a stapler performance issue is defined as a failure of the powered circular stapler (study device) to perform per its IFU. This includes but is not limited to difficulty placing or removing the stapler, stapler misfire/failure of the device to fully fire, staple line defects, incomplete or thin donuts, tissue damage, positive intraoperative leak test, detached components, unformed staples, or any other device failure.

No formal hypothesis will be tested in this study.

## **5.6 ANALYSIS SETS**

The primary analysis of safety and effectiveness endpoints will be performed on the Full Analysis Set, defined as all subjects who are enrolled in the study and have an anastomosis attempted with the powered circular stapler. A Per Protocol analysis set will be defined as all subjects who had an anastomosis completed with the powered circular stapler and no major protocol deviations. Effectiveness analyses will be repeated for the Per Protocol Set.

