## **3.0 INVESTIGATIONAL PLAN**

### **3.1 OVERALL STUDY DESIGN AND PLAN - DESCRIPTION**

Patients scheduled to undergo a left-sided colon resection, and who meet study entry criteria, may be enrolled. In an effort to minimize selection bias, patients will be consecutively screened for enrollment. All subjects who meet entry criteria will be encouraged to enroll in the study. A subject will be considered enrolled once their anastomosis has been attempted with the powered circular stapler.

Procedures may be performed open or MIS according to institutional standard-of-care (SOC). Use of a hand port and robotic assistance are permissible providing the powered circular stapler is used to create the anastomosis. Conversion from MIS to open surgery is permissible under the protocol at the surgeon's discretion for the patient's safety. Follow-up care will be documented post-operatively to confirm healing of the anastomosis.

The final scheduled study visit will occur 28 days post-procedure (routinely scheduled follow-up with surgeon). Follow-up by phone for subjects is permissible when an on-site visit is not planned or more than six weeks post-operative.

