## **6 Analysis Sets**

The summary of safety and effectiveness endpoints will be performed on the set of enrolled subjects in whom an anastomosis was attempted with the ECHELON CIRCULAR™ Powered Stapler. This will be labeled the Full Analysis Set. This set of subjects will be identified by having answered “Yes” to the question “Was anastomosis attempted?” on the Intraoperative Data eCRF.

The summary of effectiveness endpoints will be repeated on the set of subjects in the Full Analysis Set who also have no major protocol deviations. This will be labeled the Per Protocol Set.

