System Organ Class 4	Preferred Term 1	xx (xx.x%)
	Preferred Term 2	xx (xx.x%)
		xx (xx.x%)

The following tables will have the same format as Table 11:

Table 12	All Serious Adverse Events by System Organ Class and Preferred Term Full Analysis Set
Table 13	Adverse Events Related to the Study Device by System Organ Class and Preferred Term Full Analysis Set
Table 14	Serious Adverse Events Related to the Study Device by System Organ Class and Preferred Term Full Analysis Set
Table 15	Adverse Events Related to the Study Procedure by System Organ Class and Preferred Term Full Analysis Set
Table 16	Serious Adverse Events Related to the Study Procedure by System Organ Class and Preferred Term Full Analysis Set

Table 17  
 Protocol Deviations  
 Full Analysis Set

Characteristics	Overall (N = ##)
Total Number of Protocol Deviations	xxx
Specific Types of Protocol Deviations [1]	
Informed Consent Process	xx (xx.x%)
Inclusion/Exclusion Criteria	xx (xx.x%)
Study Procedure	xx (xx.x%)
Visit Out of Window	xx (xx.x%)
Other	xx (xx.x%)
Sponsor Assessment of Protocol Deviations [1]	
Minor	xx (xx.x%)
Major	xx (xx.x%)
Number (%) of Subjects With at Least 1 Protocol Deviation [2]	xx (xx.x%)

1. Denominator used is the total number of protocol deviations reported.
2. Denominator used is the total number of subjects in the column header.

The following tables will have the same format as Table 7:

Table 18	Technical Issues Summary Per Protocol Analysis Set
Table 19	Technical Issues Summary Surgical Approach – Open Laparotomy Full Analysis Set
Table 20	Technical Issues Summary Surgical Approach – Hand-assisted MIS Full Analysis Set
Table 21	Technical Issues Summary Surgical Approach – Laparoscopy Full Analysis Set
Table 22	Technical Issues Summary Surgical Approach – Robotic Full Analysis Set
Table 23	Technical Issues Summary Surgical Indication – Colorectal Carcinoma Full Analysis Set
Table 24	Technical Issues Summary Surgical Indication – Ulcerative Colitis Full Analysis Set
Table 25	Technical Issues Summary Surgical Indication – Diverticulitis Full Analysis Set
Table 26	Technical Issues Summary Surgical Indication – Crohn's Disease Full Analysis Set
Table 27	Technical Issues Summary Surgical Indication – Colorectal polyps or polyp syndrome Full Analysis Set
Table 28	Technical Issues Summary Subjects With Any Potential Anastomotic Leak Risk Factor From Medical History eCRF Full Analysis Set

The following tables will have the same format as Table 11:

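### Protocol 5.6 admits only anastomoses completed with the powered stapler to the Per Protocol Set, so failures that prevent completion drop out of the repeat analysis; SAP 6 omits this condition without saying so

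*Protocol*

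**What the plan says.** Protocol 5.6 puts the main analysis on everyone in whom an anastomosis was attempted: "The primary analysis of safety and effectiveness endpoints will be performed on the Full Analysis Set". It then defines a Per Protocol Set as "all subjects who had an anastomosis completed with the powered circular stapler and no major protocol deviations" and adds: "Effectiveness analyses will be repeated for the Per Protocol Set".

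The primary endpoint (Protocol 2.1 and 5.5) is the number of subjects with a stapler performance issue. The listed issues include "stapler misfire/failure of the device to fully fire" and a catch-all for other failures of the device.

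SAP 6 defines the Per Protocol Set differently, as "subjects in the Full Analysis Set who also have no major protocol deviations". Completion is not mentioned. SAP Table 18 repeats the primary endpoint summary in this set. SAP Table 6 has a category for an anastomosis that was not completed, so the event is foreseen in the data, but neither document gives an expected number.

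Protocol 5.1 says that the SAP is to supplement the analysis described in the protocol. The SAP does not say that its Per Protocol definition departs from Protocol 5.6, and gives no reason for the departure.

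**The concern.** Completing the anastomosis with the powered stapler is a result of how the device performed, and device performance is what the endpoint measures. If the stapler fails to fire and the anastomosis is finished another way, or not at all, the Protocol rule removes that subject because of the very event being counted. This is selection on the outcome.

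What is at stake is the supportive result. Table 18 is the only planned repeat of the primary endpoint in an alternative analysis set; Tables 19 to 28 are subgroups. SAP 8.4.1 intends qualitative comparison with published rates, which Protocol 5.7 puts at 15% to 20%, and Protocol 1.0 expects the powered device to have fewer technical issues. A Per Protocol rate lowered by its own entry rule would lean towards that expectation.

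The two documents also leave it unclear which definition governs.

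**Working it through.** **Inputs.** n = 165 and an expected rate of 15% to 20% (Protocol 5.7, SAP 7); exact Clopper-Pearson 95% interval (SAP 8.4.1). The number of non-completers is not given, so it is an assumption below.

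**The plan's own figure.** The one-sided 95% margin is 1.645 × √(p(1 − p)/165). At p = 0.15 it is 4.57%, and at p = 0.20 it is 5.12%. This agrees with the stated maximum of 5.1%, which is not in dispute and serves here only as a yardstick.

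**Formula.** Let x be the Full Analysis Set subjects with an issue, k the non-completers removed, and j those among the k who had an issue.

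- Per Protocol rate = (x − j)/(165 − k).
- It lies below x/165 only if j/k > x/165, that is, only if issues are more common among non-completers than overall.
- One removed subject with an issue changes the rate by −(1 − x/165)/164. This is −0.8/164 = −0.49 points at x = 33, and −0.848/164 = −0.52 points at x = 25.

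**Upper bound of the fall: every removed subject had an issue (j = k).**

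| k removed | from 33/165 = 20.0% | from 25/165 = 15.2% |
|---|---|---|
| 1 | 32/164 = 19.5% | 24/164 = 14.6% |
| 3 | 30/162 = 18.5% | 22/162 = 13.6% |
| 5 | 28/160 = 17.5% | 20/160 = 12.5% |
| 10 | 23/155 = 14.8% | 15/155 = 9.7% |

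With k = 5, the exact 95% interval moves from 14.2–26.9% to 12.0–24.3% in the first column, and from 10.1–21.5% to 7.8–18.6% in the second. With k = 10 the fall is 5.2 to 5.5 points, about the plan's margin. That case needs 10/33 = 30% or 10/25 = 40% of all issues to have prevented completion, which nothing in the documents supports.

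**Other mixes, k = 5.**

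- One of the five had an issue: 32/160 = 20.0% and 24/160 = 15.0%, almost no change.
- None of the five had an issue: 33/160 = 20.6% and 25/160 = 15.6%, so the rate rises.

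**Under SAP 6.** There is no completion condition, so k = 0 on this ground and the shift is zero.

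**The case against.** The strongest reply is that the criticised rule is not the one that generates Table 18. That table exists only in the SAP, which is the plan for the final analysis, and SAP 6 has no completion condition. This stands. A reader might infer that Table 18 as specified is biased by completion; the SAP does not support that.

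A reader might also try to bring the exclusion back through protocol deviations. Protocol 3.1 contains the words "providing the powered circular stapler is used to create the anastomosis", but there they qualify the permission to use hand ports and robotic assistance. They do not make finishing by another method after a device failure a deviation. Protocol 3.10 treats a stapler issue as something to record, with the action taken and whether it worked. Likewise, "Visit Out of Window" in SAP Table 17 is only a type of deviation; minor or major is graded separately, and nothing makes a late visit major. What remains is narrower: neither document defines a major deviation, and Table 17 leaves the grading to the sponsor, so no written rule prevents such an exclusion either.

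The reply also limits the reach of the Protocol rule. A misfire followed by completion with a powered stapler stays in the set. So do positive leak tests, staple line defects and thin donuts in completed anastomoses. The primary estimate uses all attempted anastomoses, no hypothesis is tested, and Table 6, Table 7 and Listing 11 show non-completions and issues in full.

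None of this removes the defect in Protocol 5.6 or the unexplained difference between the documents.

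**Conclusion.** The point holds for Protocol 5.6. Its completion condition removes stapler failures that prevent completion from an analysis of stapler failure. The Per Protocol rate then tends to be biased low, provided that issues are more common among non-completers than overall. That is plausible, because device failure is a direct cause of non-completion, but it is not certain.

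The size cannot be computed from the documents. It is about 0.5 points for each removed subject with an issue, and 2.5 to 2.7 points for five such subjects. These figures assume that all removed subjects had an issue, so for a given number removed they are the largest possible fall.

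Two stronger readings are tempting and not supported. One is that the Per Protocol rate can only look better than the Full Analysis Set rate; removing subjects without an issue raises it. The other is that all the most serious failures are removed; only those that prevent completion with a powered stapler are.

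The Full Analysis Set estimate is untouched. The matter concerns a supportive, descriptive analysis and two definitions that must be reconciled.

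**What to change.** Delete the completion requirement from Protocol 5.6, so that its Per Protocol Set matches SAP 6: membership of the Full Analysis Set and no major deviation. In both documents, state that non-completion, or a change of method after a stapler issue, is not by itself a major deviation that excludes a subject from the Per Protocol Set. Without the second statement, aligning the definitions would leave the same exclusion open to case-by-case grading.

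The cost is a short edit to each document, with no new data and no change to the primary analysis. The small downside is that the Per Protocol rate may look slightly less favourable.

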## **5.7 SAMPLE SIZE JUSTIFICATION**

A total of 165 eligible subjects are planned to be enrolled in up to 12 sites to ensure at least 150 subjects complete the study. No formal hypothesis is being tested in this study, thus the sample size was not statistically sized through a power calculation, but rather is considered sufficient for a descriptive summary of stapler performance issues through confidence interval estimation and evaluation of safety. The sample size of 165 subjects is consistent with the amount of information that was planned to be collected on the powered stapler in the original study design and provides acceptable precision for estimation of the rate of stapler performance issues. Available literature suggests that stapler performance issues are observed in 15% to 20% of subjects in whom a circular stapler is used, and a sample size of 165 subjects will provide a margin of error for a one-sided 95% confidence interval that does not exceed 5.1% for estimation of the true rate of stapler performance issues. This margin of error will be even smaller should the expected rate be lower than 15% to 20%.

Further, in consideration of rare AEs that may occur, for an event that occurs at a rate of, for example, 1.5%, then in a sample of 165 subjects, the probability of observing at least 1 event is greater than 90% under a binomial probability model. Thus, this sample size provides a high probability of observing rare events if they do occur and provides reasonable assurance that the absence of such events in the study is not a result of too few subjects being studied, should none be observed.

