### **Primary and Secondary Endpoint Analyses**

The primary endpoint of stapler performance issues will be summarized by counts and percentages and a 95% confidence interval will be calculated.

Summary statistics as appropriate for continuous or categorical variables will be provided for assessments of surgical stress as measured by SURG-TLX, and a surgeon satisfaction questionnaire.

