## **5 Levels of Significance**

No hypotheses are specified for this study and no p-values are being calculated, therefore no level of significance is specified. All estimation of endpoints will be performed using 95% confidence intervals.

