## 7 Sample Size Justification

A total of 165 eligible subjects was planned to be enrolled in up to 12 sites to ensure at least 150 subjects complete the study. No formal hypothesis was being tested in this study, thus the sample size was not statistically sized, but rather was considered sufficient for a descriptive summary of stapler performance issues through confidence interval estimation and evaluation of safety. The sample size of 165 subjects was consistent with the amount of information that was planned to be collected on the powered stapler in the original study design and provides acceptable precision for estimation of the rate of stapler performance issues. Available literature suggests that stapler performance issues are observed in 15% to 20% of subjects in whom a circular stapler is used, and a sample size of 165 subjects will provide a margin of error for a one-sided 95% confidence interval that does not exceed 5.1% for estimation of the true rate of stapler performance issues.

Further, in consideration of rare AEs that may occur, for an event that occurs at a rate of, for example, 1.5%, then in a sample of 165 subjects, the probability of observing at least 1 event is greater than 90% under a binomial probability model. Thus, this sample size provides a high probability of observing rare events if they do occur and provides reasonable assurance that the absence of such events in the study is not a result of too few subjects being studied, should none be observed.

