## 8.4 Primary and Secondary Endpoints and Associated Hypotheses

### 8.4.1 Primary Endpoint and Associated Hypotheses

No formal hypotheses are specified for this study. The study endpoints are representative of endpoints that are currently reported in the available literature for stapler performance and this will allow for qualitative comparisons with the results from this study.

The primary performance endpoint in this study is the percentage of subjects who experienced a failure of the ECHELON CIRCULAR™ Powered Stapler to perform per its IFU. This includes but is not limited to difficulty placing or removing the stapler, stapler misfire/failure of the device to fully fire, staple line defects, incomplete or thin donuts, tissue damage, positive intraoperative leak test, detached components, unformed staples, or any other device failures.

The denominator for the primary endpoint will be the total number of subjects where an anastomosis was attempted and the numerator will be the number of subjects who experienced a stapler performance issue. An exact 95% confidence interval using the Clopper-Pearson method will also be estimated.

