Side to Side	xx (xx.x%)
Anastomosis not completed	xx (xx.x%)
Type of Stapler Used	
ECHELON CIRCULAR Power Stapler (diameter 29 mm)	xx (xx.x%)
ECHELON CIRCULAR Power Stapler (diameter 31 mm)	xx (xx.x%)

*Programming note: Denominator for Conversion to open is number of subjects with surgical approach of hand-assisted MIS, laparoscopy, and robotic.*

Table 6  
Intra-Operative Information  
Full Analysis Set

Characteristic	Overall (N = ##)
Estimated Distance of Anastomosis From Anal Verge	
n	xx
Mean (SD)	xx.x (xx.x)
Median (Min, Max)	xx.x (xx, xx)
Adjunct used	
Yes	xx (xx.x%)
No	xx (xx.x%)
Type of Adjunct used	
Seamguard	xxx
E vicel fibrin sealant	xxx
Other fibrin sealant	xxx
Surgifoam hemostat	xxx
Surgicel hemostat	xxx
Oversew	xxx
Other	xxx
Intra-op Leak Test Result	
Leak	xx (xx.x%)
No Leak	xx (xx.x%)
Conversion to Open Procedure?	
Yes	xx (xx.x%)
No	xx (xx.x%)
Relationship of Conversion to Study Device?	
None	xx (xx.x%)
Possibly related	xx (xx.x%)
Possibly related	xx (xx.x%)

*Programming note: Denominator for Conversion to open is number of subjects with surgical approach of hand-assisted MIS, laparoscopy, and robotic.*

Table 7  
Technical Issues Summary  
Full Analysis Set

Characteristic	Overall (N = ##)
Number of Subjects With At Least One Technical Issue [1]	
Yes, n (%)	xx (xx.x%)
95% Exact Confidence Interval	xx.x%, xx.x%
Number of Technical Issues Observed	xxx
Technical Issue Category [2]	
Difficulty placing the stapler	xx (xx.x%)
Difficulty coupling anvil to stapler	xx (xx.x%)
Stapler misfire	xx (xx.x%)
Difficulty removing the stapler	xx (xx.x%)
Staple line defects	xx (xx.x%)
Incomplete or thin donuts	xx (xx.x%)
Tissue damage	xx (xx.x%)
Positive intraoperative leak test	xx (xx.x%)
Detached components	xx (xx.x%)
Malformed/unformed staples	xx (xx.x%)
Other device failure	xx (xx.x%)
Technical Issue Related to an Adverse Event?	
Yes	xx (xx.x%)
No	xx (xx.x%)
Intra-operative Related complications	
Yes	xx (xx.x%)
No	xx (xx.x%)

[1] Percentage is calculated using total number of subjects where anastomosis was attempted as the denominator.

[2] Percentage is calculated using number of technical issues observed as the denominator.

*Programming note: Only technical issue categories actually observed need be displayed.*

Table 8  
Surg-TLX Questionnaire  
Full Analysis Set

Characteristic	Overall (N = ##)
Overall Score	
n	xx
Mean (SD)	xx.x (xx.x)
Median (Min, Max)	xx.x (xx, xx)
Mentally Fatiguing	
n	xx
Mean (SD)	xx.x (xx.x)
Median (Min, Max)	xx.x (xx, xx)

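### The 5.1% margin that supports 165 subjects belongs to a one-sided interval, while the planned two-sided exact interval has a half-width of 6.4 points (upper arm 6.9) at a 20% rate

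*Protocol*

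**What the plan says.** Protocol 5.7 states that the study was not sized by a power calculation and that 165 subjects give acceptable precision for the rate of stapler performance issues. It takes from the literature that "stapler performance issues are observed in 15% to 20% of subjects in whom a circular stapler is used", and then gives the precision: "165 subjects will provide a margin of error for a one-sided 95% confidence interval that does not exceed 5.1" percent. SAP 7 repeats the claim: "margin of error for a one-sided 95% confidence interval that does not exceed 5.1% for estimation of the true rate of stapler performance issues".

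The analysis sections describe a different interval:

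- Protocol 5.8 (primary and secondary endpoint analyses) says the primary endpoint will be "summarized by counts and percentages and a 95% confidence interval will be calculated", without naming method or sidedness.
- SAP 5 says: "All estimation of endpoints will be performed using 95% confidence intervals".
- SAP 8.4.1 names the method: "An exact 95% confidence interval using the Clopper-Pearson method will also be estimated".
- The Table 7 shell in the SAP appendix has a row labelled "95% Exact Confidence Interval" with two placeholders, one for each limit.

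No one-sided interval or bound appears in the analysis sections or table shells of either document.

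**The concern.** The justification and the analysis differ in two ways. The stated margin is one-sided and the interval to be reported is two-sided. The stated margin also comes from a normal approximation, whereas the SAP specifies the exact method, which is wider here on the upper side. Both differences make the stated precision look better than the reported interval will be.

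This matters because the study is purely estimative. With no hypothesis and no power calculation, the width of the interval is the quantitative argument for 165 subjects on the primary endpoint. SAP 8.4.1 also intends the result to be set beside published rates qualitatively, and the true width governs how far such a comparison can go. A reader who takes 5.1 points at face value would expect an observed 20% to carry an upper limit near 25%; the planned interval puts it near 27%.

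**Working it through.** **Inputs**

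- n = 165 (Protocol 5.7, SAP 7). SAP 8.4.1 takes as denominator all subjects with an anastomosis attempted, and enrolment is defined by that attempt, so the denominator is 165 if enrolment goes as planned.
- Assumed rate p: 15% to 20% (Protocol 5.7, SAP 7).
- Stated margin: not above 5.1%, one-sided, 95% (Protocol 5.7, SAP 7).
- Planned interval: Clopper-Pearson, 95%, two printed limits (SAP 8.4.1, Table 7).

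**Step 1: reproduce the stated figure.** One-sided normal-approximation margin, z(0.95) × √(p(1 − p)/n):

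- p = 0.20: 1.645 × √(0.16/165) = 1.645 × 0.03114 = 0.0512, or 5.12 points.
- p = 0.15: 1.645 × √(0.1275/165) = 1.645 × 0.02780 = 0.0457, or 4.57 points.

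The value at 20% matches the stated 5.1, so the arithmetic is right for the interval it describes.

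**Step 2: change the sidedness only.** Two-sided normal approximation, 1.960 × √(p(1 − p)/n):

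- p = 0.20: 1.960 × 0.03114 = 6.10 points.
- p = 0.15: 1.960 × 0.02780 = 5.45 points.

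**Step 3: change the method only.** One-sided 95% Clopper-Pearson bounds at 33/165 (20.0%): the upper bound is 25.82%, which is 5.82 points above the estimate; the lower bound is 15.01%, which is 4.99 points below it. The exact method alone exceeds 5.1 on the upper side and stays within it on the lower side.

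**Step 4: the interval actually planned.** For x events in n, the two-sided 95% Clopper-Pearson limits are the 0.025 quantile of Beta(x, n − x + 1) and the 0.975 quantile of Beta(x + 1, n − x).

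| Observed | Exact 95% CI | Below estimate | Above estimate | Half-width |
|---|---|---|---|---|
| 25/165 (15.2%) | 10.1% to 21.5% | 5.10 | 6.40 | 5.75 |
| 33/165 (20.0%) | 14.2% to 26.9% | 5.81 | 6.92 | 6.37 |

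The half-width exceeds 5.1 at every count from 25 to 33. It falls to about 5.1 only near an 11% rate (18/165: 5.05), and the upper arm only near 7% (12/165: 5.09).

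**Step 5: size of the understatement at 20%.**

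- Half-width: 1 − 5.1/6.37 = 20%.
- Upper arm: 1 − 5.1/6.92 = 26%.

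For scale, a 5.1-point margin at a 20% rate would take about 237 subjects by the two-sided normal approximation, 255 by the exact half-width and 290 by the exact upper arm. These numbers show how far apart the two statements are; they are not a proposal to enlarge the study.

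**The case against.** The strongest reply is that nothing is miscalculated or hidden. The figure is openly labelled one-sided and is correct for that label, and neither document promises a two-sided half-width of 5.1. That stands as far as it goes: this is a mismatch between two sections, not a computing error. The label does not cure it, because the margin it describes belongs to an interval the trial never reports.

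A second reply is that the larger figures are chosen selectively. Part of this stands. The lower arm at 25/165 is 5.10, equal to the stated figure, and the one-sided exact lower margin at 20% is 4.99. The half-width is therefore the fairer headline, and it exceeds 5.1 across the assumed range. The upper arm deserves separate mention because the upper limit is the one that matters for a rate of device problems.

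Third, precision is not the only basis for 165. The protocol also cites the amount of information planned in the original design, and a probability above 90% of seeing at least one event at a 1.5% rate, which reproduces (1 − 0.985^165 = 91.7%). That is true, but the first is not a quantitative argument and the second concerns rare adverse events, not the primary endpoint.

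Finally, the consequence is limited. There is no hypothesis, p-value or decision rule, no precision threshold is set, and the SAP already fixes the correct interval, so the results will be the same whatever the justification says. That stands, and it bounds the weight of the point. The 150 completers should not be used to enlarge it either: completion refers to follow-up, whereas the primary endpoint is intra-operative and counts every attempted anastomosis.

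**Conclusion.** The concern holds. The stated margin describes a one-sided normal-approximation interval; the trial will report a two-sided exact one. At an observed 20% the planned half-width is 6.4 points against the stated 5.1, with an upper arm of 6.9; at about 15% the half-width is 5.7 and the upper arm 6.4.

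This rests on two readings. The first is that the planned interval is two-sided: the documents never use that word, but it follows from an unqualified 95% interval with two printed limits. The second is that the denominator is the planned 165. The exact method is named only in the SAP, but the two-sided normal margin at 20% (6.1) also exceeds 5.1, so the conclusion does not depend on the method. The effect is overstated precision in the sample-size rationale; error rates, power and the adequacy of 165 subjects for a descriptive study are not in question.

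**What to change.** Keep 165 subjects and the Clopper-Pearson analysis. In SAP 7, and in Protocol 5.7 if the protocol is revised for any reason, delete the one-sided statement and put in its place wording such as:

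*With 165 subjects, the two-sided exact (Clopper-Pearson) 95% confidence interval has a half-width of about 5.7 points at an observed rate near 15% and 6.4 points at 20%; at 20% the upper limit lies 6.9 points above the estimate.*

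The cost is wording only: no added subjects, data or analyses, and a slightly less favourable precision statement. A protocol amendment for this alone would need sponsor issue and ethics approval at each site, and the SAP already describes the design largely in the past tense. If the protocol is no longer open to change, a correction in the SAP or a note in the clinical study report is enough.
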